Title: Pain Inflammation and Cannabis in HIV

NCT05554146

IRB#: 2021-13662

IRB Approval Date: 10/22/2025

1) Background and Significance

1. A. Specific Aims

There is an explosive increase in medical cannabis use in the United States (US).¹ Medical cannabis is legal in 37 states, and severe pain and HIV are qualifying conditions in most states.¹ In New York (NY), all medical cannabis products have precise dosing of its two main active components, THC and CBD.^{2,3} Medical cannabis products in NY are oil-based (e.g., soft-gel capsules), making dosing and titration easily measurable. Thus, NY offers a unique opportunity to conduct studies to study how medical cannabis use affects pain in PLWH.

PLWH have a high burden of pain,⁴⁻¹¹ and most commonly experience neuropathic pain.^{12,13} The etiology of neuropathic pain in PLWH is complex. It is related to persistent systemic inflammation from HIV infection regardless of VL suppression,¹⁴ with increased pro-inflammatory cytokines (TNF α , IL-6) and decreased anti-inflammatory cytokines (IL-4, IL10).¹⁵ These same cytokines are related to psychological symptoms in PLWH, which are deeply interrelated with neuropathic pain.¹⁶⁻²¹ Neuropathic pain is associated with poor HIV outcomes, including poor antiretroviral (ARV) adherence,²² virologic failure,²³ and poor retention in care.^{10,23} Despite this, little is known about its optimal management.¹² Current treatment modalities for neuropathic pain in PLWH carry many associated risks, prompting investigations into novel therapies, such as medical cannabis.¹²

In two randomized trials of PLWH, cannabis reduced neuropathic pain more than placebo.^{24,25} While existing studies are informative,^{24,25} **critical gaps remain in our understanding of how cannabis alleviates neuropathic pain in PLWH.** Studies have not evaluated how different THC/CBD content impacts pain and have not used products comparable to available medical cannabis products.²⁶ Additionally, studies in PLWH had short follow up time (5-12 days) and no longitudinal outcomes. The mechanism of cannabis's analgesia in PLWH with neuropathic pain remains unknown. No studies have examined how cannabis interacts with the complex relationship of psychological symptoms, inflammation, and neuropathic pain in PLWH.

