The benefits of cannabis may be offset by its adverse events.²⁷ Cannabis is linked to psychological symptoms including anxiety, depression,²⁸ and psychotic symptoms.²⁹ In some studies, cannabis use is associated with poor ARV adherence and virologic failure;³⁰ in others, this is not the case.³¹ No studies have examined how THC/CBD content contributes to adverse events (psychological symptoms, poor ARV adherence, and virologic failure).

Our overarching goal is to test how medical cannabis use affects neuropathic pain, with particular attention to THC/CBD content and adverse events. We propose an observational cohort study of 100 PLWH with (a) neuropathic pain, (b) active certification for medical cannabis, and (c) intent of being dispensed soft-gel capsule products at a medical cannabis dispensary (including high THC: low CBD product and high CBD:low THC product). Over 14 weeks, participants will have 2 in-person visits and 15 phone-based questionnaires (one at baseline, and every week for 14 weeks). Data sources will be blood and urine samples, questionnaires, and medical and pharmacy records. The primary independent variable will be the type of soft-gel capsule product. The secondary independent variable will be reported cumulative THC and CBD dose. The primary outcome will be self-reported pain severity.³² Secondary outcomes will be pro-inflammatory cytokines (TNF α , IL-6), anti-inflammatory cytokines (IL-4, IL-10),¹⁵ psychological symptoms (symptoms of depression,³³ anxiety,³⁴ and psychosis³⁵), ARV adherence, and VL. Among PLWH with neuropathic pain, we will:

Aim 1: Examine how medical cannabis use affects self-reported pain. *H1:* The effect of medical cannabis use on self-reported pain-severity will differ by THC/CBD content.

Aim 2: Examine how medical cannabis use affects pro- and anti-inflammatory cytokines.

H2: Medical cannabis that has higher THC content will have greater reduction in pro-inflammatory cytokines (TNF α , IL-6). *H3:* Medical cannabis that has higher CBD content will have greater increase in anti-inflammatory cytokines (IL-4, IL-10).

Aim 3: Examine how medical cannabis use affects adverse events. *H4:* Participants who use high THC (vs. high CBD) cannabis products will have more psychological symptoms, poorer ARV adherence, and less suppressed VL.

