In-person visits: Participant's 2 in-person visits will occur in private rooms at the Montefiore/Einstein ICTR Clinical Research Center. At the baseline visit, study staff will describe the study and obtain written informed consent. Tracking forms as well as agreements to release medical, pharmacy, and PMP records will be completed. Participants will receive a refillable debit card for compensation. At all in-person visits, we will administer questionnaires, and collect blood and urine samples. Participants will receive \$27.50 for each in-person visit.

Phone or web visits will occur weekly over 14 weeks and include brief (5-7 minute) questionnaires administered by study staff over the phone or completed on-line. A total of 15 visits will occur, the first at baseline, when participants can be trained on how to complete it, and then one at the end of each week of the follow-up period. Participants will receive \$3 on debit cards after completing each phone or web-based questionnaire.

Blood draws will occur at week 0 and 14 in-person visits. They will measure VL, CD4 count, pro- and anti-inflammatory cytokines. Participants will be compensated an additional \$15 for each visit in which there is a blood draw.

Main independent variable will be the soft gel capsule product dispensed at Vireo, including a 1) high THC capsule, or 2) high CBD capsule. Other key independent variables will be cumulative THC and CBD taken (weeks 3-14, continuous measures).

Main outcome variables: Our primary outcome is pain severity, measured via the BPI severity scale (ordinal variable), as recommended by a committee of international pain experts.⁹² It is an 11-point (0-10) numerical rating scale of pain intensity, where 0 is 'No pain' and 10 is 'Pain as

bad as you can imagine'. Participants will complete the BPI severity scale in each phone visit (baseline and at each weekly visit).

Pro- (TNF α , IL-1 β , IL-6) and *anti-* (IL-4, IL-10) *inflammatory cytokines (secondary outcomes;* 0, 14 week *blood draws*) will be measured with Luminex assay and reported as picograms per mm 3 (continuous measure).

Adverse events (secondary outcomes) will be ARV adherence (AIDS Clinical Trial Group [ACTG] Adherence Interview,^{93,108} Adherence Visual Analog Scale [VAS; weekly]),⁹⁴ VL suppression (blood draws at 0, 14 weeks; copies/mL); and psychological symptoms—depression (CES-D; 0 and 14 weeks),⁹⁵ anxiety (GAD-7; 0 and 14 weeks),^{96,94,97,109}

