Aim 1: Examine how medical cannabis use affects self-reported pain. H1: The effect of medical cannabis use on self-reported pain-severity will differ by THC/CBD content. The primary outcome will be change in BPI pain severity scale (ordinal variable, 0-10; measured at baseline and weekly for 14 weeks). A clinically significant change is 30% reduction in BPI pain severity scale.⁹² Secondary measures will include BPI pain interference scale and neuropathic pain (painDETECT). We will compare the proportion of participants who achieve clinically significant change in pain at 14 weeks between those who use high THC soft gel capsules and those who use high CBD soft gel capsules. BPI pain interference scale and painDETECT will be compared between those using high THC vs high CBD as well. We will use mixed-effects logistic regression to test the effect of study arm on pain relief across the course of the study. Results will be adjusted for covariates associated with the outcomes of interest on bivariate testing. We will repeat this model using alternative measures of medical cannabis (cumulative dose of THC and CBD).

Aim 2: Examine how medical cannabis use affects pro- and anti-inflammatory cytokines. H2: Medical cannabis that has higher THC content will have greater reduction in pro-inflammatory

cytokines ($TNF\alpha$, $IL-6$). *H3: Medical cannabis that has higher CBD content will have greater increase in anti-inflammatory cytokines ($IL-4$, $IL-10$).* We will examine how pro- and anti-inflammatory cytokines measured at 0 and 14 weeks change in participants using high THC products versus high CBD products. We will use mixed-effects linear regression analyses to examine intervention and time effects as well as intervention-by-time interactions. This approach is appropriate in the event that the pro- and anti-inflammatory cytokine data show a non-normal distribution. We will repeat this model using alternative measures of medical cannabis (cumulative dose of THC and CBD). We will adjust for other chronic conditions that may lead to change in inflammatory cytokines, such as obesity, cardiovascular disease, and diabetes.

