Aim 3: Examine how medical cannabis use affects adverse events. *H4: Participants who use high THC (vs. high CBD) cannabis products will have more psychological symptoms, poorer ARV adherence, and less suppressed VL.* We will examine whether participants using high THC products vs high CBD products have a greater chance of adverse events, including psychological symptoms, ARV adherence, and VL. We will use mixed-effects linear regression analysis for continuous measures (VL, ARV adherence, and psychological symptoms). Each adverse event (Table 8) will be included in a separate model. We will repeat this model using alternative measures of medical cannabis (cumulative dose of THC and CBD).

Aim 4: Explore mechanisms by which medical cannabis promotes analgesia. *H5: Different doses of THC and CBD will have differing effects on inflammatory cytokines, psychological symptoms, and ultimately analgesia.*

We will use a pooled analysis of THC and CBD, using weekly questionnaires and PMP records. We will examine these relationships longitudinally in a stepwise process. First, we will conduct a mixed-effects model to examine how potential mediators lead to analgesia (reduction in BPI severity score). We will repeat analyses for possible mediators, including inflammatory cytokines and psychological symptoms. We will also determine if exposures influence changes in these variables over time, which in turn, influence change in analgesia (e.g., using time-lagged mediators and outcomes). Mediators found to be significant will be included in the final model.⁹² We will calculate the standardized total effect from the exposures to analgesia as well as the standardized mediational (i.e., indirect) effects via mediators. The mediational effect is calculated as the product of the effect from the exposures to the mediators, and the effect from the mediators to the outcome.

8) Data quality control and database management

Data management: Questionnaire, medical records, and PMP data will be de-identified and entered by study staff into a password-protected computer and database. Paper records will be stored in a locked filing cabinet that only research staff can access. Medical and PMP record data will be de-identified and entered in a secure HIPAA compliant web-based system. To protect confidentiality, we will use separate processes for ID- and name-based files and seek a certificate of confidentiality.

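### If participants adjust dose to their pain, the cumulative-dose analyses can show a dose-pain association when dose has no effect

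*Combined protocol and SAP*

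**What the plan says.** Section 1.A describes the design: "We propose an observational cohort study of 100 PLWH". No section assigns a dose. Section 1.A also gives cumulative dose its role: "The secondary independent variable will be reported cumulative THC and CBD dose". Section 2.C sets the window: "Other key independent variables will be cumulative THC and CBD taken (weeks 3-14, continuous measures". It does not say whether this is one total per person or a running sum. Titration is mentioned once, in Section 1.A, where the oil-based products are described as "making dosing and titration easily measurable".

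In Section 7.A the Aim 1 model is: "We will use mixed-effects logistic regression to test the effect of study arm on pain relief across the course of the study". Dose is then substituted for product: "We will repeat this model using alternative measures of medical cannabis (cumulative dose of THC and CBD". The same sentence appears under Aims 2 and 3. For Aim 4 the plan states: "We will use a pooled analysis of THC and CBD, using weekly questionnaires and PMP records". It goes on to total and indirect effects on analgesia.

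The Aim 1 covariate rule is: "Results will be adjusted for covariates associated with the outcomes of interest on bivariate testing". Section 7.A also names age, sex and comorbidities if they are unequal between arms, and chronic conditions for Aim 2. Pain reported during follow-up is not named as a covariate for any dose model.

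**The concern.** Dose is chosen week by week, by people who rate their pain week by week. Someone still in pain may take more; someone relieved may stay low; someone who gets no benefit may stop. Last week's pain can then influence this week's dose, and it also predicts this week's pain. That makes it a confounder arising after baseline, which no baseline covariate can remove. If dose does work, earlier pain is also on the path from earlier dose to later pain, so simply adding it beside a cumulative dose is not a full answer either.

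A single weeks 3-14 total has a further weakness when it is used for weekly scores: part of the dose was taken after the score that it is meant to explain.

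At stake are the dose versions of Aims 1 to 3 and H5, which is worded in terms of effects. Titration could be reported as a dose effect, hide a real benefit, or suggest harm.

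**Working it through.** **1. The plan's own figure.** Section 3.A and Table 9 give power only for the product comparison; there is no power or error rate for the dose analyses. As a check on the repeated-measures setting, take effective n per arm = 42m / (1 + (m-1) x ICC). With m = 14 weekly scores and ICC = 0.4 this is 588 / 6.2 = 94.8. For 40% vs 20%, two-sided 5%, power is 0.858 (stated 0.84). ICC 0.3 and 0.2 give 0.927 and 0.979 (stated 0.91 and 0.97). The table is reproduced to within 2 points.

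**2. Inputs.** From the documents: 84 analysed (42 per arm), weekly pain, dose window weeks 3-14, response defined as a 30% reduction, two-sided 5%, a mixed-effects logistic model, ICC 0.4. Assumed, because the documents give none: how strongly dose follows pain. The true dose effect is zero throughout, so any rejection above 5% is error.

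**3. Setting A.** Binary weekly relief with about 30% responders; random-intercept logistic model; likelihood-ratio test; 300-500 runs. Dose steps up each week with probability p_no after a week without relief and p_yes after a week with relief.

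| Feedback (p_no / p_yes) | Weeks 3-14 total | OR per SD, total | Running dose, week in model |
|---|---|---|---|
| None | 3-7% | - | 4-5% |
| Weak (0.25 / 0.15) | 32-33% | 0.77 | 6% |
| Moderate (0.30 / 0.10) | 81-84% | about 0.61 | 7-9% |
| Strong (0.40 / 0.05) | 100% | 0.46 | 12% |

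An OR below 1 means that more dose goes with fewer responders. With week-to-week pain persistence (rho 0.6), running dose gave 20% (moderate, OR 1.21) and 30% (strong, OR 1.38).

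**4. Setting B.** The odds of a step-up multiply by exp(slope) per point of last week's pain: exp(0.25) = 1.28, exp(0.5) = 1.65.

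| Analysis | Slope 0 | Slope 0.25 | Slope 0.5 |
|---|---|---|---|
| Total, planned mixed logistic (150 runs) | 11% | 83% | 100% |
| Same, separate simulation (100 runs) | 13% | 91% | 100% |
| Week-14 pain on strictly earlier dose (100 runs) | 6% | 68% | 100% |

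In the 150-run set the median OR per SD was 1.0, 0.44 and 0.26. The Monte Carlo standard error at 68% is sqrt(0.68 x 0.32 / 100) = 4.7 points. The total already exceeds 5% at slope 0, so feedback accounts for about 91 - 13 = 78 points at slope 0.25. The week-14 row uses only earlier dose, so reverse time order is not the whole problem.

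Running dose to week t-1, with week, in the random-intercept model gave 10-11% with or without feedback in one set of runs. Another gave 12-15% (13% without feedback), and a third 12.5-16% (12.5% without). A variant with improvement spread over 14 weeks reached 18%.

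**5. Sign and time.** If people without relief stop more often (8% vs 2% per week), the total-dose model rejects in 28% of runs with OR 1.28, so the sign reverses. With running dose, week omitted and pain improving over time, rejection is 92% with no feedback at all.

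**6. Candidate remedies.** A sequential conditional mean model held the error at 3-7%. Inverse-probability weights on past dose lowered it from 17% to 4% (weak), 52% to 10% (moderate), 51% to 8% (moderate, rho 0.6) and 89% to 17% (strong, rho 0.6).

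**The case against.** The strongest reply has four parts.

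- **The premise is inferred.** The documents say that titration can be measured, not that participants set dose by pain. This stands. The error rates are conditional on assumed behaviour.
- **The planned model copes with a sensible exposure.** A random intercept absorbs stable differences between people. With running lagged dose and week in the model, feedback added little in most settings. This stands too. A reader might infer that every cumulative-dose model fails badly. A GEE without a person-level effect does reject far more often for running dose, but the plan specifies a mixed model, so such rates should not be charged to it. The plan does not, however, commit to running dose or name a week term for Aim 1. One total is the most literal reading of the stated window.
- **The scope is limited.** The primary contrast is by initial product, which later dose changes cannot alter. Cumulative dose is secondary and Aim 4 is exploratory. This stands. A reader might extend the figures to cytokines, mood, adherence and viral load, but only pain was simulated; those outcomes are affected only where pain is linked to them. Sections 1.A and 1.B do assert such links.
- **Aim 4 already mentions time-lagged mediators and outcomes.** That orders mediator before outcome. It does not deal with pain changing dose, so this part does not answer the concern.

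A reader might also conclude that the dose analyses will show a false association, and always towards less relief. The documents support neither: behaviour is unknown, and plausible alternatives reverse the sign.

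**Conclusion.** The concern holds in conditional form. If dose responds to pain, the secondary dose models and Aim 4 can report an association that titration or stopping alone produces. For a weeks 3-14 total in the planned mixed logistic model the false-positive rate was about 32-100%. For week-14 pain on earlier dose it was about 68-100%. Running dose with week is much safer: about 6-16% in most settings, and 20-30% with strongly persistent pain.

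These figures rest on a true null, 84 participants and assumed titration strengths. The direction of bias cannot be predicted from the documents. The primary analysis is not in question. The plan should still be changed, because following it as written allows the most vulnerable choice of exposure.

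**What to change.** In Section 7.A:

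- State whether cumulative dose is a total or a running sum, and do not use the weeks 3-14 total as the exposure for weekly pain.
- For weekly pain, use only dose taken before each score, include week, and adjust for the previous week's pain and dose and for baseline BPI. A sequential conditional mean model fitted by GEE with independence working correlation is one way. State that it estimates a short-term dose effect.
- For total dose against week-14 outcomes, either add a sensitivity analysis with inverse-probability weights built from prior weekly pain, or report a descriptive association and not an effect.

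Weekly pain and reported dose are already collected, so the cost is SAP wording and some extra analysis. The drawbacks are real. The estimate is short-term, not cumulative. Questionnaires fall at week end, so dose changes in response to pain within the same week remain uncontrolled. Weights need truncation and leave some bias at about 84 participants (8-17% error under moderate to strong feedback).

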Aims 1-4	Medical cannabis use	Initial soft-gel capsule dispensed at Vireo Certification for medical cannabis (date, doctor, conditions) All medical cannabis products dispensed (date, product, dose, amount dispensed) Self-reported medical and unregulated cannabis use (product, # of days used, route, dollar amount of unregulated cannabis purchased, ASI)	PR MR PR TQ
Primary outcome variables			
Aims 1, 4	Pain Severity	Brief Pain Inventory (BPI) Severity subscale ⁹⁰	TQ
Secondary outcome variable			
Aims 2, 4	Inflammatory cytokines	Pro-inflammatory cytokines (TNF α , IL-6) Anti-inflammatory cytokines (IL-4, IL-10)	B B
Aims 3, 4	Adverse events	VL, CD4 count AIDS Clinical Trial Group (ACTG Adherence) ⁹³ , Visual Analog Scale (VAS) ⁹⁴ ARVs dispensed Depression (Center for Epidemiological Studies-Depression Scale [CES-D])), Generalized Anxiety Disorder (GAD-7) ⁹⁶	B IQ PR IQ
Other measures			
Aims 1-4	Sociodemographics	Age, race/ethnicity, education, insurance, sex, gender	IQ
Aims 1-4	Pain characteristics	Brief Pain Inventory (BPI) Interference subscale ⁹⁰ Pain catastrophizing scale ⁹⁸ , Pain DETECT questionnaire ⁸⁴	IQ IQ
Aims 1-4	Pain treatment	Pain treatment (SSRIs, gabapentin, injections, physical therapy)	IQ/MR/PR
Aim 3	Substance use/disorder	Smoking (Fagerstrom test for nicotine dependence) ⁹⁹ , Alcohol Use Disorders Identification Test (AUDIT) ¹⁰⁰ , ASI ⁹⁷	IQ
Aim 3	HIV Risk Behaviors	HIV risk behaviors (HIV Risk-taking Behavior Scale ¹⁰¹⁻¹⁰³)	IQ
Aims 3, 4	Psychiatric symptoms	PTSD Checklist (PCL), ¹⁰⁴ Insomnia severity index, ¹⁰⁵	IQ
Aims 1, 3, 4	Quality of Life	Roland Morris Disability Questionnaire ¹⁰⁶ , Patient Reported Outcomes Quality of Life-HIV (PROQOL-HIV) ¹⁰⁷	IQ
Aims 1-4	Medical comorbidities	Comorbidities (obesity, cardiovascular disease, diabetes)	MR
Aims 1-4	Side effect vs benefit	Treatment Satisfaction Questionnaire for Medication (TSQM-9) ⁹¹	TQ
Aims 1-4	Urine cannabinoid	Urine GCMS for cannabinoids	

B=blood test; MR=Medical records; PR=Pharmacy records or Prescription Monitoring Program; IQ= in-person questionnaire; TQ=phone questionnaire; SSRI=selective serotonin reuptake inhibitor; TQ measures occur every week; IQ occurs at 0 and 14 weeks. B occurs at 0 at 14 weeks.

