4. Study records will be kept in locked files and/or within limited access, code-protected computer files, available only to the investigators and study personnel.
5. Publication or presentation of study results will not identify subjects by name.

In addition to addressing issues of confidentiality, it is crucial that we protect participants from emotional distress that may occur during research visits. All visits will occur in medical facilities. If emotional distress occurs during research visits an on-site physician will assess the patient. Per clinical judgment, the participant will either be referred to the Emergency Room or to their treating physicians the following day.

6.C. Potential benefits.

Neuropathic pain in PLWH is associated with poor HIV outcomes, including poor ARV adherence,³² virologic failure,³³ and poor retention in care.^{19,33} PLWH experience a high burden of pain,⁴⁻¹¹ and most commonly experience neuropathic pain.^{12,13} Medical cannabis has known analgesic properties in PLWH with neuropathic pain.^{24,25} Participants in our study will have been evaluated by their own physicians and deemed to be appropriate to receive medical cannabis based on those standards already. By participating in this study, they may experience benefit from medical cannabis use by experiencing improved pain. They may experience increased attention from research staff during the study period, resulting in improved pain, psychological, and HIV outcomes.

7) Data Analysis

7.A Data Analyses: *Intention-to-treat principle* will be used in primary analyses. If key variables (age, sex, medical comorbidities) are unequal among arms, we will conduct adjusted analyses. We will also conduct per-protocol analyses; medical cannabis use for at least 3 months of products will represent sufficient study participation.

Missing data: We will conduct multiple imputations using Markov Chain Monte Carlo imputation methods. Results from multiple imputed data sets will be pooled into a single dataset. We will compare statistical results using datasets with imputed values and the dataset that drops missing values.

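### Entered as main effects, obesity, cardiovascular disease and diabetes would not adjust the Aim 2 product-by-time test of H2 and H3; the plan should state their interactions with time

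*Combined protocol and SAP*

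**What the plan says.** Section 1.A describes the design: "We propose an observational cohort study of 100 PLWH with" neuropathic pain and current medical cannabis certification. Product is not randomised.

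Section 7.A, Aim 2, sets the comparison: "We will examine how pro- and anti-inflammatory cytokines measured at 0 and 14 weeks change in participants using high THC products versus high CBD products". The model is: "We will use mixed-effects linear regression analyses to examine intervention and time effects as well as intervention-by-time interactions". The covariate sentence follows in the same paragraph: "We will adjust for other chronic conditions that may lead to change in inflammatory cytokines, such as obesity, cardiovascular disease, and diabetes". No covariate-by-time term and no regression of change on covariates is named, and the form in which the conditions enter is not stated.

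Section 2.C fixes the number of cytokine visits at two: "Blood draws will occur at week 0 and 14 in-person visits". Its table of measures lists "Comorbidities (obesity, cardiovascular disease, diabetes") with the medical record as source and describes no repeat measurement, so each condition is in effect one value per participant.

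Section 7.A also has a general rule for the primary analyses: "If key variables (age, sex, medical comorbidities) are unequal among arms, we will conduct adjusted analyses". It too leaves the form of adjustment open.

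**The concern.** H2 and H3 are about change: a greater fall in TNF-alpha and IL-6, and a greater rise in IL-4 and IL-10. In a model with product, time and their interaction, the interaction carries that contrast. The plan names three conditions because of their possible influence on cytokine change. The only interaction it names, however, is product-by-time, and adjusting for a covariate ordinarily means adding a main effect. A main effect of a fixed covariate acts on level and cannot act on change.

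At stake is the meaning of an adjusted H2 or H3 result in a non-randomised comparison. A paper could report the product effect on cytokine change as adjusted for comorbidity when the coefficient is simply the raw difference in mean change.

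**Working it through.** **Inputs from the documents.** Two cytokine visits, weeks 0 and 14 (section 2.C). Tested contrast: product difference in change (section 7.A, Aim 2). 50 per product group, 42 after 15% attrition, and ICC 0.4 (section 3.A).

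**Inputs assumed.** Prevalence of each condition by product group, and the effect of a condition on 14-week change. The documents give neither.

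**The plan's own figure.** The only figure for Aim 2 is power above 90% for d = 0.5 with 42 per group at ICC 0.4. For change between two visits it does not reproduce: SD of change = √(2 × (1 − 0.4)) = 1.095, SE = 1.095 × √(2/42) = 0.239, 0.5/0.239 = 2.09, power about 55% at 5% two-sided. That is a separate matter, and nothing below depends on it.

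**Step 1, main effects only.** With g for product and x for the conditions:

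- week 0: y0 = a + b·g + e′x
- week 14: y14 = (a + c) + (b + d)·g + e′x
- difference: y14 − y0 = c + d·g

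x has gone. With both visits present, the estimate of d is the raw difference in mean change, with or without x.

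**Step 2, conditions by time.** If the conditions act on change, week 14 contains (e + f)′x and the difference is c + d·g + f′x. For one condition, leaving out f′x biases d by f × (difference in prevalence between product groups).

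**Step 3, size of that bias, in SD (all inputs assumed).**

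| Prevalence gap | Extra change 0.2 SD | 0.5 SD | 0.8 SD |
|---|---|---|---|
| 10 points | 0.02 | 0.05 | 0.08 |
| 20 points | 0.04 | 0.10 | 0.16 |
| 30 points | 0.06 | 0.15 | 0.24 |

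If the condition affects level only, f = 0 and the bias is 0.

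**Step 4, simulation.** Random-intercept REML model, ICC 0.4, true product effect on change 0. Each of the three conditions has prevalence 45% against 20%, and diabetes adds 0.5 SD to change, so the expected bias is 0.25 × 0.5 = 0.125. There were 3,000 data sets per case.

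| Case | Quantity | Unadjusted | Main effects | Conditions by time |
|---|---|---|---|---|
| Both visits, 42 per group | Mean estimate | 0.126 | 0.126 | −0.004 |
| | Rejection at 5% | 8.3% | 8.3% | 5.5% |
| | Mean SE | 0.243 | 0.243 | 0.270 |
| 50 per group, 15% missing week 14, no imputation | Mean estimate | 0.130 | 0.130 | 0.004 |
| | Rejection at 5% | 8.6% | 8.8% | 5.8% |
| | Mean SE | 0.237 | 0.236 | 0.262 |

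With both visits present, the largest difference between the first two columns' estimates over all data sets was 3 × 10⁻¹⁵, that is, rounding error. In one such set the estimate was 0.317 (SE 0.236) both unadjusted and with main effects, and −0.181 (SE 0.234) with condition-by-time terms. An unstructured covariance also left estimate and SE unchanged by the main effects (0.2135, SE 0.3124). With 15% missing, main effects moved individual estimates by 0.018 SD on average (at most 0.085) and left the mean bias in place.

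**Step 5, missing data.** Section 7.A plans multiple imputation. Each imputed set has both visits, so within it the cancellation is exact. The conditions could still act through the imputation model, whose contents are not listed.

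**The case against.** The strongest reply is that the defect is inferred. The plan lists effects to be examined, not a complete model, and never says that the conditions enter as main effects. If condition-by-time terms are intended, the analysis is sound. This stands: a reader might infer that the plan specifies an ineffective adjustment, but the text leaves the form open. What remains is that the ordinary reading gives an adjusted test identical to the unadjusted one, and nothing in the text rules that reading out.

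Second, cancellation does no harm unless the conditions drive change over 14 weeks. The plan's sentence can be read as being about cytokine levels. In a simulation with a level effect of 0.5 SD, prevalence 40% against 15%, 42 per group and ICC 0.4, the mean bias was −0.002 with or without the main effect. This also stands, and nothing in the documents quantifies an effect on change.

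Third, a reader might infer that H2 and H3 have no other protection against confounding. The documents do not support that. Section 7.A has the general rule on age, sex and comorbidities. The eligibility criteria exclude recent NSAID use, certain steroid use and recent COVID vaccination, among others. Comparing within-person change also removes stable differences in level.

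Fourth, the repeat models use cumulative THC and CBD dose. If dose enters as zero at week 0 with no separate baseline dose term, covariate main effects do move the dose estimate. The plan does not give that form, so the present point is confined to the product-by-time test.

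Fifth, extending the point to all of Aim 3 would go too far. Aim 3 names no time interaction and no change score, H4 can be read as a contrast of levels, and the adherence visual analogue scale is weekly.

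**Conclusion.** The point holds as a gap in specification with a definite consequence. If obesity, cardiovascular disease and diabetes enter Aim 2 as main effects, the product-by-time test of H2 and H3 is not adjusted for any effect they have on 14-week change. That part is algebra: exact with both visits present, close to exact with 15% dropout. The same applies to any covariate fixed over time that is added under the general rule of section 7.A, when product-by-time in a two-visit model is the tested term.

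The size is not established. It is 0.02 to 0.24 SD over the assumed ranges, and zero if the conditions affect level only. In the simulated case the bias of 0.126 is about half the standard error of 0.243, and rejection under no product effect rises from 5.5% to 8.3%. A reader might take this for a serious flaw in the study. The documents do not support that, because cytokines are secondary outcomes and the size rests wholly on assumed inputs. It is a cheap improvement to a secondary analysis.

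**What to change.** Add one sentence to section 7.A, Aim 2: obesity, cardiovascular disease and diabetes enter the model together with their interactions with time. With both visits present, regressing the week 0 to week 14 change on product and these conditions is equivalent. Use the same form for any covariate added to that test under the general rule of section 7.A. In Aim 3, apply it only to two-visit outcomes that are tested through change. If condition-by-time terms were intended all along, the sentence simply records that.

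The cost is about three degrees of freedom and no new data. Where the conditions are unbalanced between products there is also some loss of precision: in the simulated case with both visits present, the standard error rose from 0.243 to 0.270, or 11%. Settling the form before analysis avoids a later choice between two models that can give different answers.
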